11.1.4 Response Criteria

11.1.4.1 Evaluation of Target Lesions

Complete Response (CR): Disappearance of all target lesions. Any pathological lymph nodes (whether target or non-target) must have reduction in short axis to <10 mm.

Partial Response (PR): At least a 30% decrease in the sum of the diameters of target lesions, taking as reference the baseline sum diameters.

Progressive Disease (PD): At least a 20% increase in the sum of the diameters of target lesions, taking as reference the smallest sum on study (this includes the baseline sum if that is the smallest on study). In addition to the relative increase of 20%, the sum must also demonstrate an absolute increase of at least 5 mm. (Note: the appearance of one or more new lesions is also considered progressions).

Stable Disease (SD): Neither sufficient shrinkage to qualify for PR nor sufficient increase to qualify for PD, taking as reference the smallest sum diameters while on study.

11.1.4.2 Evaluation of Non-Target Lesions

Complete Response (CR): Disappearance of all non-target lesions and normalization of tumor marker level. All lymph nodes must be non-pathological in size (<10 mm short axis).

Note: If tumor markers are initially above the upper normal limit, they must normalize for a patient to be considered in complete clinical response.

Non-CR/Non-PD: Persistence of one or more non-target lesion(s) and/or maintenance of tumor marker level above the normal limits.

Progressive Disease (PD): Appearance of one or more new lesions and/or *unequivocal progression* of existing non-target lesions. *Unequivocal progression* should not normally trump target lesion status. It must be representative of overall disease status change, not a single lesion increase.

Although a clear progression of “non-target” lesions only is exceptional, the opinion of the treating physician should prevail in such circumstances, and the progression status should be confirmed at a later time by the review panel (or Principal Investigator).

11.1.4.3 Evaluation of Best Overall Response

The best overall response is the best response recorded from the start of the treatment until disease progression/recurrence (taking as reference for progressive disease the smallest measurements recorded since the treatment started). The patient's best response assignment will depend on the achievement of both measurement and confirmation criteria.

For Participants with Measurable Disease (i.e., Target Disease)

Target Lesions	Non-Target Lesions	New Lesions	Overall Response	Best Overall Response when Confirmation is Required*
CR	CR	No	CR	> 4 wks Confirmation**
CR	Non-CR/Non-PD	No	PR	≥4 wks Confirmation**
CR	Not evaluated	No	PR	
PR	Non-CR/Non-PD/not evaluated	No	PR	
SD	Non-CR/Non-PD/not evaluated	No	SD	Documented at least once > 4 wks from baseline**
PD	Any	Yes or No	PD	no prior SD, PR or CR
Any	PD***	Yes or No	PD	
Any	Any	Yes	PD	

* See RECIST 1.1 manuscript for further details on what is evidence of a new lesion.
 
** Only for non-randomized trials with response as primary endpoint.
 
*** In exceptional circumstances, unequivocal progression in non-target lesions may be accepted as disease progression.
 
Note: Participants with a global deterioration of health status requiring discontinuation of treatment without objective evidence of disease progression at that time should be reported as “symptomatic deterioration.” Every effort should be made to document the objective progression even after discontinuation of treatment.
				

For Participants with Non-Measurable Disease (i.e., Non-Target Disease)

Non-Target Lesions	New Lesions	Overall Response
CR	No	CR
Non-CR/non-PD	No	Non-CR/non-PD*
Not all evaluated	No	not evaluated
Unequivocal PD	Yes or No	PD
Any	Yes	PD

* ‘Non-CR/non-PD’ is preferred over ‘stable disease’ for non-target disease since SD is increasingly used as an endpoint for assessment of efficacy in some trials so to assign
		

this category when no lesions can be measured is not advised
--

11.1.5 Duration of Response

Duration of overall response: The duration of overall response is measured from the time measurement criteria are met for CR or PR (whichever is first recorded) until the first date that recurrent or progressive disease is objectively documented (taking as reference for progressive disease the smallest measurements recorded since the treatment started, or death due to any cause. Participants without events reported are censored at the last disease evaluation).

Duration of overall complete response: The duration of overall CR is measured from the time measurement criteria are first met for CR until the first date that progressive disease is objectively documented, or death due to any cause. Participants without events reported are censored at the last disease evaluation.

Duration of stable disease: Stable disease is measured from the start of the treatment until the criteria for progression are met, taking as reference the smallest measurements recorded since the treatment started, including the baseline measurements.

11.1.6 Treatment Beyond Progression

Immunotherapeutic agents such as Pembrolizumab may produce antitumor effects by potentiating endogenous cancer-specific immune responses. The response patterns seen with such an approach may extend beyond the typical time course of responses seen with cytotoxic agents, and can manifest as a clinical response after an initial increase in tumor burden or even the appearance of new lesions.

If radiologic imaging shows progressive disease (PD), tumor assessment may be repeated by the site approximately 4 weeks later in order to confirm continued PD with the option of continuing treatment per below while awaiting radiologic confirmation of progression. If repeat imaging shows a reduction or stabilization in the tumor burden compared to the initial scan demonstrating PD, treatment may be continued as per treatment calendar. If repeat imaging confirms continued PD, patients will be discontinued from study therapy. If reimaging is no worse than the prior scan 4 weeks prior, patients may continue therapy and be reimaged in another 8 weeks. If evidence for continued, increasing progression with subsequent imaging, the patient will be discontinued. In determining whether or not the tumor burden has increased or decreased, investigators should consider all target lesions as well as non-target lesions. The decision to continue study treatment after the first evidence of disease progression determined by radiologic imaging is at the Investigator's discretion based on the clinical status of the patient as described in the table below.

Patients may receive study treatment while waiting for confirmation of continued PD if they are clinically stable as defined by the following criteria:

- Absence of signs and symptoms (including worsening of laboratory values) indicating disease progression
- No decline in ECOG performance status
- Absence of rapid progression of disease
- Absence of progressive tumor at critical anatomical sites (e.g., cord compression) requiring urgent alternative medical intervention

Table 7. Treatment Beyond Progression

	Clinically Stable		Clinically Unstable	
	Imaging	Treatment	Imaging	Treatment
1 st radiologic evidence of PD	Repeat imaging at approximately 4 weeks to confirm PD	May continue study treatment at the Investigator's discretion while awaiting confirmatory scan	Repeat imaging at approximately 4 weeks to confirm PD if possible	Discontinue treatment
Repeat scan confirms PD	No additional imaging required	Discontinue treatment	No additional imaging required	N/A
Repeat scan shows SD, PR, or CR	Continue regularly scheduled imaging assessments every 12 weeks	Continue study treatment at the Investigator's discretion	Continue regularly scheduled imaging assessments every 12 weeks	May restart study treatment if condition has improved and/or clinically stable per Investigator's discretion
Tumor imaging will be assessed every 12 weeks (84 ±7 days).				

11.1.7 Progression-Free Survival

Overall Survival: Overall Survival (OS) is defined as the time from randomization (or registration) to death due to any cause, or censored at date last known alive.

Progression-Free Survival: Progression-Free Survival (PFS) is defined as the time from randomization (or registration) to the earlier of progression or death due to any cause. Participants alive without disease progression are censored at date of last disease evaluation.

Time to Progression: Time to Progression (TTP) is defined as the time from randomization (or registration) to progression, or censored at date of last disease evaluation for those without progression reported.

11.2 Antitumor Effect

11.2.1 Anti-Tumor Effect Using irRECIST

Definition of Tumor Response Using Immune-Related Response Criteria (irRC)

The sum of the longest diameter of lesions (SPD) at tumor assessment using the immune-related response criteria (irRC) for progressive disease incorporates the contribution of new measurable lesions. Each net Percentage Change in Tumor Burden per assessment using irRC criteria accounts for the size and growth kinetics of both old and new lesions as they appear.

Definition of Target Lesions Response Using irRC

irComplete Response (irCR): Complete disappearance of all target lesions. This category encompasses exactly the same participants as “CR” by the mWHO criteria.

irPartial Response (irPR): Decrease, relative to baseline, of 50% or greater in the sum of the products of the two largest perpendicular diameters of all target and all new measurable lesions (i.e., Percentage Change in Tumor Burden). Note: the appearance of new measurable lesions is factored into the overall tumor burden, but does not automatically qualify as progressive disease until the SPD increases by $\geq 25\%$ when compared to SPD at nadir.

irStable Disease (irSD): Does not meet criteria for irCR or irPR, in the absence of progressive disease.

irProgressive Disease (irPD): At least 25% increase Percentage Change in Tumor Burden (i.e., taking SPD of all target lesions and any new lesions) when compared to SPD at nadir.

Definition of Non-Target Lesions Response Using irRC

irComplete Response (irCR): Complete disappearance of all non-target lesions. This category encompasses exactly the same participants as “CR” by the mWHO criteria.

irPartial Response (irPR) or irStable Disease (irSD): non-target lesion(s) are not considered in the definition of PR; these terms do not apply.

irProgressive Disease (irPD): Increases in number or size of non-target lesion(s) does not constitute progressive disease unless/until the Percentage Change in Tumor Burden increases by 25% (i.e., the SPD at nadir of the target lesions increases by the required amount).

Impact of New Lesions on irRC

New lesions in and by themselves do not qualify as progressive disease. However their contribution to total tumor burden is included in the SPD which in turn feeds into the irRC criteria for tumor response. Therefore, new non-measurable lesions will not discontinue any participant from the study.

Definition of Overall Response Using irRC

Overall response using irRC will be based on these criteria:

Immune-Related Complete Response (irCR): Complete disappearance of all tumor lesions (target and non-target together with no new measurable/unmeasurable lesions) for at least 4 weeks from the date of documentation of complete response.

Immune-Related Partial Response (irPR): The sum of the products of the two largest perpendicular diameters of all target lesions is measured and captured as the SPD baseline. At

each subsequent tumor assessment, the SPD of the two largest perpendicular diameters of all target lesions and of new measurable lesions are added together to provide the Immune Response Sum of Product Diameters (irSPD). A decrease, relative to baseline of the irSPD compared to the previous SPD baseline, of 50% or greater is considered an immune Partial Response (irPR).

Immune-Related Stable Disease (irSD): irSD is defined as the failure to meet criteria for immune complete response or immune partial response, in the absence of progressive disease.

Immune-Related Progressive Disease (irPD): It is recommended in difficult cases to confirm PD by serial imaging. Any of the following will constitute progressive disease:

At least 25% increase in the SPD of all target lesions over baseline SPD calculated for the target lesions.

At least a 25% increase in the SPD of all target lesions and new measurable lesions (irSPD) over the baseline SPD calculated for the target lesions. (Hodi, Hoos et al. 2008) (Wolchok et al., 2009)

Table 10. Immune-Related Response Criteria Definitions

Target Lesion Definition	Non-Target Lesion Definition	New Measurable Lesions	New Unmeasurable Lesions	Percent change in tumor burden (including measurable new lesions when present)	Overall irRC Response
Complete Response	Complete Response	No	No	−100%	irCR
Partial Response	Any	Any	Any	≥ −50%	irPR
				<−50% to <+25%	irSD
				>+25%	irPD
Stable Disease	Any	Any	Any	<−50% to <+25%	irSD
				>+25%	irPD
Progressive Disease	Any	Any	Any	≥+25%	irPD

Immune-Related Best Overall Response Using irRC (irBOR)

irBOR is the best confirmed irRC overall response over the study as a whole, recorded between the date of first dose until the last tumor assessment before subsequent therapy (except for local palliative radiotherapy for painful bone lesions) for the individual participant in the study. For the assessment of irBOR, all available assessments per participant are considered.

irCR or irPR determinations included in the irBOR assessment must be confirmed by a second (confirmatory) evaluation meeting the criteria for response and performed no less than 4 weeks after the criteria for response are first met.

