2.3.3 Rationale for Endpoints

2.3.3.1 Efficacy Endpoints

The primary endpoint of this study is to determine the safety, tolerability and recommended dosing for the combination of pembrolizumab plus trebananib. Our secondary objective are to obtain in preliminary fashion the efficacy of the combination including PFS at 6 months, the rate of 1-year overall (OS), the response rate (RR) and time to progression in diseases where anti-angiogenesis had shown to be effective. Chest, abdomen, and pelvic CT scan will be obtained every twelve weeks for determination of therapeutic efficacy. Standard solid tumor response criteria (RECIST) will be obtained. To further explore the clinical observations in some patients receiving ipilimumab of delayed responses and disease burden increasing before stable disease or response attained, we will incorporate proposed immune response criteria to assess for clinical activity. These immune response criteria (irRC) (Hodi, Hoos et al. 2008) (Wolchok et al., 2009) will be captured and compared to standard response criteria for solid tumors.

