11. MEASUREMENT OF EFFECT

11.1 Antitumor Effect – Solid Tumors

Although the clinical benefit of these drugs has not yet been established, the intent of offering this treatment is to provide a possible therapeutic benefit, and thus the patient will be carefully monitored for tumor response and symptom relief in addition to safety and tolerability. Patients with measurable disease will be assessed by standard criteria. For the purposes of this study, patients should be re-evaluated every 12 weeks (\pm 7 days). In addition to a baseline scan, confirmatory scans will also be obtained 4-6 weeks following initial documentation of an objective response.

Response and progression will be evaluated in this study using the new international criteria proposed by the Response Evaluation Criteria in Solid Tumors (RECIST) guideline (version 1.1)

[*Eur J Ca* 45:228-247, 2009]. Changes in the largest diameter (unidimensional measurement) of the tumor lesions and the shortest diameter in the case of malignant lymph nodes are used in the RECIST criteria.

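### Section 11.2.1 measures immune-related progression (irPD) from nadir in some rules and from baseline in others, so the same scan can be classified two ways

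*Combined protocol and SAP*

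**What the plan says.** Section 2.3.3.1 says that the immune response criteria "will be captured and compared to standard response criteria for solid tumors", in order to explore delayed responses and responses after an initial increase in burden. Section 11.2.1 is the only place that defines those criteria.

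Within 11.2.1 the reference for the 25% rise is as follows:

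- **Target lesions, irPR note:** new measurable lesions do not amount to progression until the sum has risen 25% from nadir.
- **Target lesions, irPD:** "taking SPD of all target lesions and any new lesions) when compared to SPD at nadir".
- **Non-target lesions, irPD:** progression only if "the SPD at nadir of the target lesions increases by the required amount".
- **Overall response, first irPD condition:** "At least 25% increase in the SPD of all target lesions over baseline SPD calculated for the target lesions".
- **Overall response, second irPD condition (target plus new measurable lesions):** "irSPD) over the baseline SPD calculated for the target lesions".
- **Table 10:** percent change in tumor burden, reference not stated.

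irPR is a fall of at least 50% from baseline in the sum of products of perpendicular diameters. irBOR is the best confirmed response over all available assessments, with irCR and irPR confirmed at least 4 weeks later.

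The section opens by describing SPD differently: "The sum of the longest diameter of lesions (SPD) at tumor assessment".

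**The concern.** Three statements use nadir, two use baseline, and no sentence ranks them. Two readers who both follow the protocol could classify the same scan differently, or the version could be chosen after the data are seen.

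What is at stake is the comparison of irRC with RECIST. RECIST progression in section 11.1.4.1 is judged against the smallest sum on study. If irPD is judged against baseline, a patient who first shrinks and then regrows can be progressing by RECIST and stable by irRC partly because the yardsticks start from different points. That could be taken for an immune response pattern.

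**Working it through.** The plan defines no irRC endpoint, sample size or power, so there is no stated figure to reproduce. The check applies the plan's own cut-offs to assumed tumor burdens in arbitrary units.

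**Inputs.** irPD: rise of at least 25% (11.2.1, both versions). irPR: fall of at least 50% from baseline (11.2.1). RECIST PD: rise of at least 20% in the sum of diameters from the smallest sum on study, and at least 5 mm (11.1.4.1). B = baseline burden, N = nadir, C = current; the values are illustrative.

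**Step 1: where the rules disagree.** The nadir rule calls irPD if C ≥ 1.25N, the baseline rule if C ≥ 1.25B. They differ when 1.25N ≤ C < 1.25B.

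| Nadir (% of baseline) | Calls differ when current burden is (% of baseline) |
|---|---|
| 30 | 37.5 to below 125 |
| 40 | 50 to below 125 |
| 50 | 62.5 to below 125 |
| 80 | 100 to below 125 |
| 90 | 112.5 to below 125 |
| 100 | never |

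**Step 2: single scans.**

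- 100/40/60: (60 - 40)/40 = +50%, irPD; (60 - 100)/100 = -40%, irSD.
- 100/30/40: (40 - 30)/30 = +33%, irPD; (40 - 100)/100 = -60%, irPR.

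**Step 3: irBOR.** For 100/40/60 the last scan confirms irPR under neither rule, so irBOR does not change. For 100/38/49, the scan at 38 is -62% and first meets irPR. The confirmatory scan at 49 is (49 - 100)/100 = -51%, which confirms irPR if the reference is baseline. It is also (49 - 38)/38 = +29%, which is irPD if the reference is nadir. irBOR changes only when the confirmatory scan is at or below -50% from baseline and at least 25% above nadir.

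**Step 4: can the two sets of rules be read as different levels?** One might take the earlier rules as lesion-level and the later ones as overall. That does not work. The target-lesion irPD rule already includes new lesions, and Table 10 feeds the target-lesion category into the overall response. If the table is read from baseline, target-lesion progression by nadir with a change below +25% has no row.

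**Step 5: against RECIST.** Assume uniform growth and no new lesions. A 25% rise in product is √1.25 - 1 = 11.8% in diameter, against 20% for RECIST. The baseline rule therefore flags progression before RECIST unless the nadir sum of diameters is below 1.118/1.20 = 0.93 of baseline, and after RECIST if it is. The 5 mm condition is set aside here.

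**The case against.** The strongest reply is that little depends on irRC. Section 11.1 bases response and progression on RECIST 1.1; ORR and PFS in 14.5 are per RECIST 1.1; the colorectal disease control rate in 14.2 uses best RECIST response. Section 14 contains no irRC analysis and defines no time-to-irPD endpoint. Section 5.12 refers progression on treatment to 11.1.6, and second-course entry in 10.5.4 uses RECIST 1.1 or iRECIST. All of this stands and limits the weight of the point. It does not remove the contradiction, because 2.3.3.1 still commits to the comparison and 11.2.1 is its only specification.

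A reader might infer three stronger things that the documents do not support:

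- **That irRC would look later than RECIST solely because of the reference point.** Step 5 shows that the direction varies: the two-dimensional 25% cut-off works towards earlier calls, and irRC also handles new lesions differently.
- **That SPD has two competing definitions and cannot be computed from the data.** The longest-diameter phrase appears once, in an introductory sentence. Both irPR definitions use products, and the overall-response text already requires those products to be captured. The unidimensional wording in 11.1 ("Changes in the largest diameter (unidimensional measurement) of the tumor lesions") describes RECIST and does not limit irRC.
- **That Table 10 reverses response and stability.** Its signs are awkward, but the text settles that a fall of 50% or more is irPR and that a rise of exactly 25% is irPD.

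**Conclusion.** The irPD rule is wrong as written, with minor to moderate weight. The current text gives two reference points, and they produce different calls for any patient whose burden first falls below baseline and then regrows into the window in step 1. Most such conflicts are irSD against irPD; some, such as 100/30/40, are irPR against irPD. Patients whose burden never falls below baseline are unaffected, so a general claim of opposite results would go too far.

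The consequence is limited to scan-level irRC calls, to irBOR in the narrow case in step 3, and to the comparison with RECIST. How many patients would be affected cannot be estimated from the documents. The example burdens are assumed, and the diameter conversions assume equal change in both dimensions.

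**What to change.** In 11.2.1, state one irPD reference and use it in the target, non-target and overall definitions. Nadir total burden, meaning target plus new measurable lesions, is the consistent choice: the section already uses nadir three times, and RECIST in 11.1.4.1 uses the smallest sum on study. Name the reference in Table 10.

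Add an order of precedence. With irPR judged from baseline and irPD from nadir, a course such as 100/30/40 meets both, so the text should say that irPD takes precedence on that scan.

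As tidying, change the introductory description of SPD to the sum of products of perpendicular diameters, and restate the Table 10 cut-offs: decrease of 50% or more is irPR; decrease under 50% to increase under 25% is irSD; increase of 25% or more from nadir is irPD.

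The cost is protocol wording and a corrected table, with no additional scans. Some irRC progressions will be dated earlier than under the baseline rule, and any scans already classified from baseline would need to be reclassified. The baseline wording is followed by two citations that could not be consulted here. If the sponsor intends baseline, the three nadir statements must change instead, and the comparison with RECIST should disclose the different reference.
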